Inclusion Criteria	
Histologic Inclusion Criteria
 
Histologic Criteria: All patients with a diagnosis of The Fibrillary GN will be classified according to the Nasr nomenclature:
 
1) Renal biopsy demonstrating DNA-JB9 Positive staining within 3 years of study randomization2) Mesangial expansion with/without glomerular sclerosis3) Membranous changes with or without diffuse sclerosis4) Crescents or endocapillary proliferation5) Level of interstitial fibrosis 
Note: Patients with > 50% interstitial fibrosis will not be eligible for study participation
 
Note: Patients with monoclonal staining of fibrillary fibers will not be eligible for study participation
 
Inclusion Criteria:
 
1) Male/Female age \geq 182) Biopsy proven Fibrillary GN within 3 years of study randomization3) Stable Maximum RAAS inhibition X 4 weeks prior to randomization 
Note: Maximum RAAS inhibition will be left to the discretion of the site PI
 
4) eGFR > 25 mls/min calculate by the CKD-EPI formula5) UP/Cr ratio \geq 2000 mg/gm

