Secondary Endpoint	Secondary Endpoints: 
1) The relative change in UP/Cr at 24 months (12 months after stopping both ACTH and Tacrolimus) in the ACTHar gel group and the ACTHar gel + Tacrolimus group.2) The percentage of patients in the ACTHar gel alone versus ACTHar gel + Tacrolimus group that achieves complete, partial or clinical responses after 12 months of therapy3) The change in eGFR (measured by CKD-EPI formula) between the ACTHar gel and ACTHar Gel + Tacrolimus groups after 24 months of treatment with ACTHar gel alone or in combination with oral Tacrolimus. In addition, we will also compare the relative change in eGFR between those patients receiving ACTHar gel alone with those randomized to combination therapy.4) To compare the change in urinary biomarkers (see below) at baseline and after 12 months of treatment with ACTHar gel alone or in combination with Tacrolimus. The patients urinary biomarker levels after 12 months of therapy will be compared between the ACTHar gel alone group and ACTHar gel + Tacrolimus group.
a) Urinary VEGF 121, 165 189, and206b) Urinary MCP-1c) Urinary Synaptopodind) Urinary TGF-betae) Urinary Podocalyxinf) Urinary Nephryn 
Fibrillary GN patients with concurrent Type II diabetes mellitus: To determine whether ACTHar gel therapy resulted in

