- **Visit 4: 14 Days Post Randomization Visit:** 14 Days Post Randomization (Visit 4) will be optional for patients traveling from long distances. Would request that patient visit nephrologist in home town if any adverse events of concern are reported.
- **Visits 5 – 7: Study Visits-Months 3 (V5), 6(V6) & 9(V7) :** We will be conducted in like manner to Randomization visit. Each patient will get a complete physical exam. Standard blood and urine studies will be performed as well as plasma, serum and urine study sample collections. Tacrolimus Trough Levels will be drawn for those patients randomized to the Tacrolimus arm.
- **Visit 8: Month 12: Primary Endpoint Evaluation:** All patients completing of 52 weeks of ACTHar gel therapy alone or in combination with Tacrolimus will be examined for their change in UP/Cr as compared to their baseline levels of urinary protein. Patients will be asked to bring 2 first morning voids of urine. These two samples will be averaged and used for

determination of the percentage of patients achieving the primary endpoint.

Complete Responders: < 300 mg/gm UP/Cr ratio

Patients that have reached this milestone will be weaned off ACTHar Gel with or without Tacrolimus over the subsequent 14 days.

Sites will start the ACTHar Gel wean at 40 units and reduce over a 2 week taper period at the discretion of the principal investigator of each site.

Non-or Partial Responders: > 50% Reduction in UP/Cr ratio to minimum value of 2000 mg/gm:

Patients will follow the same weaning protocol as the complete responders described above.

- **Visit 9: ACTHar Washout Visit:**

14 Days Post End of Treatment (Visit 9) will be optional for patients traveling from long distances and will occur after the post treatment taper. The Study Staff will request that the patient visit a Nephrologist in the patient's home town if any adverse events of concern are reported.

- **Visits 10 -12: Follow-Up Visits-Months 15 (V10), 18(V11) & 9(V12):** We will be conducted in like manner to Randomization visit. Each patient will be get a complete physical exam. Standard blood and urine studies will be performed as well as plasma, serum and urine study sample collections.

- **Visit 13: Month 24 Visit: Secondary Endpoint Evaluation:**

Patients completing 104 weeks of study participation will be evaluated for the following:

1) Percentage of Complete Responder patients weaned off ACTHar gel and Tacrolimus that developed a relapse after 12 months of no therapy.

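### Visit 8's partial-response line calls 2000 mg/gm a minimum where a ceiling was probably meant, under a label that also covers non-responders (minor)

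*Protocol*

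**What the plan says.** Under Visit 8 (Month 12) the protocol sorts patients by UP/Cr. The first group is "Complete Responders: < 300 mg/gm UP/Cr ratio". The second is headed "Non-or Partial Responders: > 50% Reduction in UP/Cr ratio to minimum value of 2000 mg/gm", and for it the text adds only "Patients will follow the same weaning protocol as the complete responders described above". No separate criterion for non-response is given.

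Secondary endpoint 2 compares the arms on the percentage of patients "that achieves complete, partial or clinical responses after 12 months of therapy", without thresholds in the endpoint itself. Nothing in the visible text says that the Visit 8 groups supply those thresholds. Visit 13, headed as the secondary endpoint evaluation, does reuse one Visit 8 label: "Percentage of Complete Responder patients weaned off ACTHar gel and Tacrolimus that developed a relapse after 12 months of no therapy".

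The UP/Cr entry threshold is 2000 mg/gm or more (Inclusion Criteria, item 5), with a 24-hour collection as an alternative route for a patient whose ratio is lower.

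Visit 8 also says that the average of two morning voids is used for "determination of the percentage of patients achieving the primary endpoint". The Primary Endpoint section, however, defines a change in UP/Cr with no threshold, and the sample size paragraph works from a difference in mean UP/Cr.

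**The concern.** Two things in the Visit 8 line do not work as printed. First, one label covers non-responders and partial responders, but its single criterion, a fall of more than 50%, describes a response. Second, a 'minimum value' of 2000 mg/gm sets, on its plain meaning, a level below which the month-12 value must not go. That excludes the larger falls, which are the better outcomes.

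If this line supplies the meaning of 'partial' for secondary endpoint 2, an analyst who programmed it literally would misclassify patients in both arms. The trial is open-label, so the direction of the limit should be settled before anyone sees results by arm.

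**Working it through.** **Inputs** (all from the protocol)
- Complete response: month-12 UP/Cr below 300 mg/gm (Visit 8).
- Partial response: fall of more than 50%, with a limit of 2000 mg/gm (Visit 8).
- UP/Cr entry threshold: 2000 mg/gm (Inclusion Criteria, item 5).
- Mean course of the 7 ACTHar-responsive patients: 5435 to 1335 mg/gm (Background).
- Mean UP/Cr in the biopsy series: 5380 mg/gm (Background; illustration only).

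The plan states no figure to reproduce here. The check is how the printed rule classifies patients.

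**Rule.** Let B be baseline and F the month-12 value. A fall of more than 50% means F < 0.5 × B. Patients with F < 300 are complete responders and are set aside.
- Floor (literal): F ≥ 2000 and F < 0.5 × B. This needs 0.5 × B > 2000, so B > 4000.
- Ceiling (likely intent): 300 ≤ F ≤ 2000 and F < 0.5 × B.

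| Baseline B | 0.5 × B | Partial if floor | Partial if ceiling |
|---|---|---|---|
| 2000 | 1000 | none | 300 to <1000 |
| 2500 | 1250 | none | 300 to <1250 |
| 4000 | 2000 | none | 300 to <2000 |
| 5380 | 2690 | 2000 to <2690 | 300 to 2000 |
| 8000 | 4000 | 2000 to <4000 | 300 to 2000 |

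On the floor, nobody with a baseline from 2000 to 4000 can qualify. The same holds for anyone who entered below 2000 by the 24-hour route.

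**The protocol's own example.** The fall from 5435 to 1335 is 1 − 1335/5435 = 75.4%. The value 1335 is not below 300, so it is not complete. It is below 2000, so on the floor it is not partial either. On the ceiling it is partial. These are group means, so the example stands for a patient who matched them.

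**Does the ceiling hang together?** The fall needed to reach 2000 is 1 − 2000/B: 60.0% at 5000, 62.8% at 5380 and 75.0% at 8000. Up to a baseline of 4000 the limit adds nothing to the 50% rule; above 4000 it is the stricter part. For example, 5380 to 2600 is a fall of 1 − 2600/5380 = 51.7%, which meets the first part and fails the second. A rule with two conditions behaves in just this way, and the example shows no contradiction.

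**The case against.** The strongest reply is that this is a slip whose meaning a sensible reader can recover. The floor would disqualify better outcomes, shut out patients at the entry threshold and reject the protocol's own responder example, so a ceiling must have been meant. Likewise, the merged heading simply gathers everyone who is not a complete responder because all follow the same wean; the criterion describes the partial group and the rest are non-responders. Most of this stands, and it is why the point is minor. It does not remove the fault: the printed word says the opposite of the likely meaning. Nor is a ceiling the only possible repair. A required absolute fall of 2000 is conceivable too, and it would exclude 3000 to 1200 (a fall of 1800), which the ceiling counts. The sponsor should confirm the meaning.

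A second reply is that the line may not serve secondary endpoint 2 at all. That also stands. Visit 13 reuses only the complete-responder label, whose threshold is not in dispute, so it does not show that the partial line is an analysis group.

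A reader might go further and infer any of the following, which the documents do not support:
- That two analysts would count almost entirely different partial responders. The two sets do barely overlap, but this requires one analyst to adopt a floor that context rejects.
- That the protocol fails to define 'clinical' response. The available text breaks off within the secondary endpoints, at "To determine whether ACTHar gel therapy resulted in", and the SAP is not shown, so absence cannot be claimed.
- That the primary endpoint is a response rate. Its own definition, the sample size paragraph and the opening sentence of Visit 8 all treat it as a change in UP/Cr; one later phrase in Visit 8 is out of step.

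**Conclusion.** The point holds as a minor wording error. Taken literally, the Visit 8 limit makes partial response impossible for every baseline from 2000 to 4000 mg/gm and leaves a 75.4% fall to 1335 mg/gm unclassified. Taken as a ceiling, which context favours, the rule is sound and only the word and the merged label need correcting.

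The consequence is conditional. It reaches secondary endpoint 2 only if the Visit 8 line is its definition of partial response and no other definition governs. The number of patients affected depends on the baseline distribution of those enrolled, which the protocol does not give, so no count is claimed. Complete response does not use the 2000 limit, and the wean is the same for both groups.

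**What to change.** 1. In the Visit 8 heading itself, separate partial responders from non-responders, and leave the weaning text as it is.
2. Before any data review, define partial response for analysis as month-12 UP/Cr not below 300 mg/gm, a reduction of more than 50% from baseline, and month-12 UP/Cr at or below 2000 mg/gm. In the heading, change 'minimum' to 'maximum'. If the sponsor did not mean a ceiling, state the intended limit instead. The remaining patients are neither partial nor complete responders, apart from those below 300 mg/gm, who are complete responders as already stated.
3. State that these criteria apply to secondary endpoint 2, and reconcile them with any response definition elsewhere in the protocol or in the SAP.
4. In Visit 8, replace the phrase about a percentage achieving the primary endpoint with: the change in UP/Cr from baseline (primary endpoint).

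The cost is wording only. The UP/Cr measurements are already scheduled, and neither the sample size nor patient management changes.

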
Number of total Clinic Visits
 
FACT-Trial: Study Design
	
conference call with the prospective patient will be arranged to discuss in details of the study; the risks/benefits of the study drug, as well as details regarding patient requirements and travel to and from the study site. The patient will be given time to review the consent with their families and other physicians.
 
If is determined by the Medical Director and the FACT Site PI that the patient is a likely candidate for the study, a travel agent will contact patient and make arrangements for airfare and overnight accommodations to visit the FACT PI. Both the airfare and overnight accommodations will be provided by NephroNet. If a patient lives within approximately 4 hours of the FACT site, they will be reimbursed for mileage and hotel. There will be a total of 13 visits per patient per site.
 
Patients agreeing to participate in the FACT sign consent at their first screening visit.
 
Thirteen (13) visits for total study: Pre-screening visits- two (2) Study Drug Treatment visits- six (6) Post Study Drug Treatment visits- five (5)
 
Study Design: This study will be a multi-center, prospective, randomized, open-labeled intervention trial of 34 patients randomized to 52 weeks of ACTHar gel alone or ACTHar gel plus oral Tacrolimus.
 
Drug Dosing:
 
Group-1: ACTHar gel alone-patients will be receive 80 units SQ Q 2X/week for 52 weeks
 
Group-2: ACTH gel 80 units 2X per week plus oral Tacrolimus (1.0 mg BID) titrating to a trough level of 4-6 ng/ml for 52 weeks
 
Note: Patient with type II diabetes will be allowed to dose at 24 units/day (0.3 mls SQ Q day) to reduce glucose fluctuations and simplify management of diabetes at the discretion of the PI.
 
Protocol-Schedule and Follow Up: Clinic Visits:

---	--

- **Visit 1: Pre-Randomization Screening & Consenting Visit:** Patients that have gone through the Pre-screening review and considered to be eligible for study participation will be seen by the local site PI for formal consenting two months prior to study randomization. The patient will then be seen by the FACT trial site PI who will perform a complete physical exam and obtain routine laboratory testing including a urine to protein Cr ratio.

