2) Percentage of patients in the ACTHar gel alone group that demonstrated additional reduction in UP/Cr

ratio following the addition of Tacrolimus at Week 52.

Hyperkalemia: Patient developing hyperkalemia defined as > 5.5 meq/L will undergo the following interventions:

Intervention #1: Review dietary sources of potassium and assess patient compliance with prescribed dietary restrictions.

Intervention #2: Adding or increasing dose of a loop diuretic. If they patient was already taking a diuretic as part of their standard of care regimen, the dose or frequency will be increased according to the discretion of the Site PI.

Intervention #3: For patients with continued hyperkalemia following intervention 1 & 2, the Site PI can consider adding a Thiazide diuretic (HCTZ or Metolazone) to the current loop diuretic.

Intervention #4: For patients with continued hyperkalemia following intervention 1 & 2 & 3, the dose of Tacrolimus can be reduced to 0.5 mg BID.

Combining Thiazide and Loop diuretic therapy to AM-PM doses

Intervention #5: For patients with continued hyperkalemia following intervention 1 & 2, 3, & 4, the patient can discontinued from Tacrolimus.

Note: Any Site PI that chooses to treat a study patient's hyperkalemia with Patiromer may do and keep the patient in the study. Any decision to use Patiromer is solely at the discretion of the Site PI.

Hyperglycemia: Patients developing intractable hyperglycemia defined as > 400 mg/dl can have their current diabetic medications modified. For patients with continued hyperglycemia despite increases in diabetic therapy, the dose of ACTHar gel can be reduced by 50%. Patients with persistent hyperglycemia can be withdrawn from the study at the discretion of the Site PI.

Note: Any Site PI choosing to use of Insulin to treat a study patient's hyperglycemia can do and keep the patient in the

study. Any decision to use institute Insulin therapy is solely at the discretion of the Site PI.

Lower Extremity Edema: Patients developing increasing lower extremity edema can have their diuretic regimen increased by either dose or frequency. Patients continuing to have edema with maximal Loop diuretics can be treated with dual Loop and Thiazide diuretic therapy. All decisions as the management of lower extremity edema will be left to the discretion of the Site PI.

Statistical Analysis Sample Size and Power.

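### Visit 13 evaluates tacrolimus added to the ACTHar-alone arm at Week 52, an addition that conflicts with treatment, visits and month-24 endpoints built on stopping therapy at month 12

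*Protocol*

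**What the plan says.** Visit 13 (Month 24 Visit: Secondary Endpoint Evaluation) lists two evaluations. Item 2 takes the ACTHar-alone group and asks what percentage had an additional reduction in UP/Cr "ratio following the addition of Tacrolimus at Week 52". It treats a change of treatment in the control arm as something that has happened.

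Other parts of the Protocol describe treatment ending at that time:

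- **Study Design:** each arm is assigned a course lasting 52 weeks.
- **Group-1 dosing:** "ACTHar gel alone-patients will be receive 80 units SQ Q 2X/week for 52 weeks".
- **Number of total Clinic Visits:** "Post Study Drug Treatment visits- five (5").
- **Visit 8 (Month 12):** complete responders are weaned over 14 days. Under "Non-or Partial Responders: > 50% Reduction in UP/Cr ratio to minimum value of 2000 mg/gm" the text reads "Patients will follow the same weaning protocol as the complete responders described above".
- **Secondary endpoint 1 and Specific Aim #2:** both place month 24 at 12 months after therapy has ended, and endpoint 1 names both groups.
- **Visit 13, item 1:** counts complete responders "that developed a relapse after 12 months of no therapy".
- **Schedule table:** month 12 is labelled end of treatment, and neither study drug nor a tacrolimus trough is marked after it.

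**The concern.** A control patient who starts tacrolimus at Week 52 is not 12 months off therapy at Week 104. For that patient, item 2 and the month-24 endpoint definitions cannot both be true.

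The stakes differ by reading. If nothing is added, the Protocol lists an evaluation to which no patient can contribute. If sites read item 2 as describing a planned step, some or all controls receive the comparator arm's extra drug during follow-up. The month-24 comparisons (secondary endpoints 1 and 3, Hypothesis #2) would remain randomized, but their meaning would change to a comparison of strategies with earlier or later tacrolimus. The Background section does not treat such an addition as neutral, since it reports a further UP/Cr reduction when tacrolimus was added in partial responders to ACTH.

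**Working it through.** There is no stated figure to reproduce. The check sets the passages side by side, with a little arithmetic.

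**1. Is Visit 13 counted as on or off treatment?** The visit count gives 2 pre-screening, 6 treatment and 5 post-treatment visits: 2 + 6 + 5 = 13. In order, these are V1–V2, V3–V8 and V9–V13. Visits 9 to 13 are therefore all off study drug.

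**2. Does the timeline agree with 12 months off therapy?** Visit 13 is at 104 weeks and treatment lasts 52 weeks: 104 − 52 = 52 weeks. From the end of the two-week taper it is 104 − 54 = 50 weeks. Both agree with endpoint 1 and Aim #2. Tacrolimus started at Week 52 does not.

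**3. What does Visit 8 do with control patients at month 12?** Complete responders are weaned. The next heading names non-responders and partial responders and applies the same wean. The criterion printed there, a reduction of more than 50%, fits partial responders only, so for true non-responders the wean rests on the heading. No group is given tacrolimus. Visit 9 is a washout visit.

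**4. Is there monitoring for tacrolimus added after month 12?** The schedule marks troughs at months 3, 6, 9 and 12, for the tacrolimus group. The text for Visits 5–7 says "Tacrolimus Trough Levels will be drawn for those patients randomized to the Tacrolimus arm". Nothing is marked for months 15 to 24 or for the ACTHar-alone group.

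**5. Is the addition provided for elsewhere?** The only other description of adding tacrolimus to ACTHar is in Background, as the result of an earlier study in membranous GN and FSGS. It is not presented as a step of this trial. The copy available to us breaks off between the secondary endpoints and the paragraph on clinic visits, so we can say only that no text shown provides for it. A provision in the missing part would not remove the conflicts in steps 1 to 4.

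**6. How many patients?** The ACTHar-alone arm has 17 planned patients.

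| Reading | Controls receiving the addition | Consequence |
|---|---|---|
| No addition | 0/17 | Item 2 cannot be evaluated |
| Addition, no eligibility rule | 1/17 = 5.9% to 17/17 = 100% | Month-24 comparisons change meaning |

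The upper end falls below 17 if complete responders stay off therapy, as item 1 implies; their share is not given.

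**7. Direction of effect.** Background reports 59% remission on ACTHar alone and over 90% after tacrolimus was added, in 22 patients: over 90 − 59 = 31 percentage points. These are other diseases. The figures show the direction the Protocol expects and are not an estimate for this trial.

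**8. A separate, related conflict.** Secondary endpoint 3 describes the eGFR change as following 24 months of treatment. The dosing text gives 52 weeks, and Hypothesis #2 speaks of 24 months of follow-up. This does not supply a Week-52 addition and does not rescue item 2.

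**The case against.** The strongest counter-argument is that item 2 is one line in a list of evaluations. It is not a treatment instruction. No dose, eligibility rule or visit supports it, and the operative text shown ends treatment at month 12, so sites are unlikely to act on it. On that view the practical cost is a descriptive item that drops out.

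Some of the evidence is also weaker than the rest:

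- A 52-week randomized course does not by itself exclude something given afterwards.
- Weaning ACTHar does not by itself exclude starting another drug.
- Item 1 concerns complete responders only.
- The trough sentence for Visits 5–7 concerns months 3 to 9.
- The lead-in to Visit 13 refers to patients completing 104 weeks. With the anticipated 10% drop-out applied to this arm, the base is nearer 17 × 0.9 = 15.3 than 17.

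Much of this is fair as to weight. The figure of 17 is an upper bound, and the range from 1 to 17 says no more than some or all. The core remains. Item 2 speaks of an addition in patients whose ACTHar is being weaned. Secondary endpoint 1, Aim #2, the count of post-treatment visits and the schedule all describe month 24 as off therapy. The line stands in the current text, and a site cannot tell whether it is a leftover. Whether controls receive a drug at Week 52 is trial conduct, so it cannot be left to an analysis plan.

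**Conclusion.** The concern holds, with high confidence as to the contradiction, and should be fixed. As written, Visit 13 item 2 either has no patients to evaluate (0 of 17) or implies a treatment change in 1 to 17 of 17 controls that alters what the month-24 UP/Cr and eGFR comparisons estimate. The size of that alteration cannot be derived from the Protocol. The month-12 primary endpoint and the sample size are unaffected under either reading. The conclusion assumes the planned 17 controls, and the statement that the addition is not provided for is limited to the text shown. Which course is clinically right after month 12 is for the sponsor to decide.

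**What to change.** Reconcile Specific Aim #2, the secondary endpoints, Study Design and Drug Dosing, the visit count, Visit 8, Visit 13 and the schedule table, and state one plan for the period after month 12.

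- **If there is no Week-52 addition:** delete Visit 13 item 2. This is one line.
- **If there is one:** state it consistently in the treatment description, Visit 8 and the schedule, including who receives it. Restate secondary endpoints 1 and 3 and Hypothesis #2/Aim #2 as a comparison of treatment strategies.

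Separately, reconcile the wording of endpoint 3 with the 52-week treatment period and with Hypothesis #2, for example by giving the assessment time as month 24 from randomization without implying a treatment duration. This is one further edit. None of these changes needs additional patients.

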Hypothesis and Specific Aims	
Hypothesis#1: A 12-month treatment with combination ACTHar gel and Tacrolimus therapy will be superior to ACTHar gel therapy alone in lowering urinary protein to creatinine (UP/Cr) ratios in patients with idiopathic DNA-JB9 positive Fibrillary GN
 
Specific Aim #1-will randomize 35 patients with biopsy proven DNA-JB9 positive Fibrillary glomerulopathy to receive a 12-month course of ACTHar gel at 80 units SQ 2X/week alone or in combination with oral Tacrolimus at 1.0 mg BID (targeting for trough Tacrolimus dose of 4-6 ng/ml).
 
Hypothesis#2: Treatment with combination ACTHar gel and Tacrolimus therapy will result in a higher eGFR after 24 months of follow up than patients randomized to ACTHar gel therapy alone
 
Specific Aim #2-will determine the change in eGFR from baseline to 24 months of follow for patients with biopsy proven DNA-JB9 positive Fibrillary glomerulopathy. It is anticipated that at 24 months (12 months after completing therapy) patients randomized to ACTHar gel plus Tacrolimus will have higher eGFR compared to patients receiving ACTHar gel alone.
 
Hypothesis #3: Combination therapy of ACTHar Gel and Tacrolimus in patients with DNA-JB9 positive Fibrillary Glomerulopathy will lead to significantly lower urinary markers of podocyte injury compared to patients receiving ACTHar gel therapy alone.
 
Specific Aim #3-will compare the relative changes in the following urinary biomarkers will be performed:
 
1. Urinary VEGF 121, VEGF-1652. Urinary VEGF-189, VEGF-2063. Urinary MCP-14. Urinary Synaptopodin5. Urinary TGF-beta6. Urinary Podocalyxin7. Urinary Nephryn 
Levels will be measured at baseline prior to treatment and after 12 months of ACTHar ge therapyl alone or in combination with oral Tacrolimus. The relative reduction urinary biomarkers will also be compared between the two treatment groups.

Study Population	
A total of 34 patients will be enrolled.
 
Group 1 (17 patients) ACTHar gel 80 units 2X/week alone for 12 months of therapy.
 
Group 2 (17 patients) ACTHar gel 80 units 2X/week plus oral Tacrolimus 1.0 mg BID titrated to trough Tacrolimus levels between 4-6 ng/ml
 
Anticipated drop out rate 10%.

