The sample size was calculated to detect a 40% difference in the mean UP/Cr ratio after 12 -month of ACTHar gel therapy alone or with oral Tacrolimus. Analysis will be intention to treat for all patient receiving at least one week of drug therapy. Based on the estimated variability of 30% for the change in UP/Cr ratio (CV) a sample size of 17 patients per arm (total-34) will be needed to provide 80% power to see a difference with a P value of < 0.05. A Fisher exact test will be applied for comparisons of adverse event frequencies. All tests were two-tailed with a P value-0.05 considered significant.

References:

- 1) Laser Microdissection and Proteomic Analysis of Amyloidosis, Cryoglobulinemic GN, Fibrillary GN, and Immunotactoid Glomerulopathy Sanjeev Sethi,* Jason D. Theis,* Julie A. Vrana,* Fernando C. Fervenza,† Anjali Sethi,‡ Qi Qian,† Patrick Quint,* Nelson Leung,* Ahmet Dogan,* and Samih H. Nasr* *Clin J Am Soc Nephrol* 8: 915–921, 2013.
- 2) Fibrillary Glomerulonephritis: A Report of 66 Cases from a Single Institution *Samih H. Nasr,* Anthony M. Valeri,† Lynn D. Cornell,* Mary E. Fidler,* Sanjeev Sethi,* Nelson Leung,‡ and Fernando C. Fervenza‡ Clin J Am Soc Nephrol* 6: 775–784, 2011.
- 3) Fibrillary Glomerulonephritis and Immunotactoid Glomerulopathy Charles E. Alpers and Jolanta Kowalewska. *J Am Soc Nephrol* 19: 34–37, 2008.
- 4) Plasmapheresis leading to remission of refractory

14March2019

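### Persistent hyperglycemia ends in withdrawal from the study, with no step that stops ACTHar gel and keeps the patient in follow-up

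*Protocol*

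**What the plan says.** The Hyperglycemia paragraph of the protocol applies to intractable glucose above 400 mg/dl and sets out a sequence:

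1. Diabetic medication can be modified.
2. If that fails, "the dose of ACTHar gel can be reduced by 50" percent.
3. If hyperglycemia persists: "Patients with persistent hyperglycemia can be withdrawn from the study at the discretion of the Site PI".

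A note beginning "Any Site PI choosing to use of Insulin to treat a study" lets the site start insulin and keep the patient in the trial.

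The Hyperkalemia steps end differently. At Intervention #5, "the patient can discontinued from Tacrolimus"; leaving the study is not mentioned.

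Three other places bear on the point:

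- **Visit 8 (month 12, primary endpoint):** "All patients completing of 52 weeks of ACTHar gel therapy alone or in combination with Tacrolimus will be examined" for change in UP/Cr.
- **Statistical Analysis Sample Size and Power:** "Analysis will be intention to treat for all patient receiving at least one week of drug therapy".
- **Schedule of visits:** UP/Cr, CMP and AE/SAE are planned at months 3 to 24, with no condition that the patient is still on drug.

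**The concern.** Stopping a drug and leaving a trial are different events. The protocol separates them for tacrolimus and hyperkalemia but not for ACTHar gel and hyperglycemia. The only named step beyond half-dose ACTHar gel takes the patient out of the study, and an unblinded investigator decides when to use it.

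The protocol itself ties this toxicity to ACTHar gel, since it halves the dose for it. It also foresees it: patients with type II diabetes not on insulin are eligible, and the Drug Dosing note offers them a daily schedule to limit glucose swings. Data would therefore go missing for a reason linked to treatment, in a study meant to compare safety as well as efficacy.

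At stake for each affected patient are the primary endpoint, the month 24 secondary endpoints and the later course of the toxicity. This cannot be left to an analysis plan, which can choose how to treat missing values but cannot collect them.

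**Working it through.** **1. The texts side by side**

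| Question | Hyperkalemia | Hyperglycemia |
|---|---|---|
| Dose cut offered | tacrolimus to 0.5 mg BID | ACTHar gel by 50% |
| Last step | stop tacrolimus | leave the study |
| Step that stops the drug and keeps follow-up | the stop does not mention leaving the study | none in the available text |

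A patient who has been through a medication change and a dose cut will almost always have had more than one week of drug, and so belongs to the intention-to-treat set. Once withdrawn, that patient has no month 12 or month 24 values. Visit 8 points the same way, because it is worded for those who complete 52 weeks of therapy. No sentence says outright that data collection stops; that is the plain reading of study withdrawal.

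**2. Inputs**

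- 17 patients per arm, 34 in total (Study Population; Statistical Analysis).
- "Anticipated drop out rate 10" percent, all causes (Study Population).
- Target difference of 40% in mean UP/Cr, taken here as a ratio of 0.60 (Statistical Analysis).
- Post-baseline UP/Cr and CMP visits at months 3, 6, 9, 12, 15, 18, 21 and 24: 8 in all (schedule).
- Assumption, not in the protocol: lost patients' UP/Cr is r times that of retained patients, with r from 0.5 to 2.

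The arm size of 17 serves only as a denominator here. The stated inputs (40% difference, 30% variability) give 10 per arm in a t-test calculation, while a standardized difference of 1.0 gives 17. That is a separate matter and does not affect this point.

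**3. Weight of one patient**

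1/17 = 5.9% of an arm. Anticipated dropout is 0.10 × 34 = 3.4 patients; hyperglycemia is an unknown part of that.

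**4. Data lost per patient**

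| Leaves just after | Visits lost of 8 | Follow-up lost |
|---|---|---|
| month 3 | 7 | 24 − 3 = 21 months |
| month 6 | 6 | 24 − 6 = 18 months |
| month 9 | 5 | 24 − 9 = 15 months |

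Months 12 and 24 are lost in every case.

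**5. Effect on the comparison**

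On the geometric-mean scale, dropping one of 17 patients changes the arm's mean by a factor r^(1/17), or its inverse depending on the arm:

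- r = 0.5: 0.5^(1/17) = 0.960
- r = 1: 1.000
- r = 2: 2^(1/17) = 1.042

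Applied to a true ratio of 0.60:

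- 0.60 × 0.960 = 0.576, a 42.4% difference
- 0.60 × 1.042 = 0.625, a 37.5% difference

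With equal losses and equal response in the two arms, the shift is zero.

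**The case against.** The strongest reply is that the text is permissive and the event is rare. Patients may be withdrawn, at the site's discretion; nothing requires it, and nothing forbids a site from stopping ACTHar gel and continuing the visits. Insulin and the dose cut are available first, insulin-dependent diabetes is excluded at entry, and patients with type II diabetes may take 24 units daily. This stands as a limit on frequency. It does not supply the missing step: insulin treats glucose without stopping the drug, and 24 units daily is 24 × 7 = 168 units a week against 2 × 80 = 160, so exposure is spread, not reduced.

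The two drugs also play different roles. Stopping tacrolimus leaves a patient on the treatment common to both arms, whereas stopping ACTHar gel leaves Group 1 on no study drug and Group 2 on tacrolimus alone. That may explain the different last steps, but intention to treat needs the later values whichever drug is stopped.

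The Visit 8 wording is weak support on its own, since saying that completers are examined does not exclude others. That is fair. ACTHar gel is given in both arms, and the protocol gives no evidence of unequal withdrawal. Finally, some pages were not available, so the absence of a follow-up rule can be asserted only for the text at hand. The Hyperglycemia paragraph itself is intact.

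**Conclusion.** The point holds. Used as written, the rule loses the month 12 UP/Cr, the month 24 eGFR and the course of the toxicity for patients whom the protocol still counts in its intention-to-treat analysis.

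The effect on the trial result is likely to be small: a factor of 0.96 to 1.04 for one excess loss in one arm, under the assumed range of 0.5 to 2 for r, and nothing if losses and responses are balanced. The number of such withdrawals is unknown and probably low. The main loss is the affected patient's own follow-up. This is a worthwhile, inexpensive improvement and not a flaw that undermines the trial.

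**What to change.** - **Hyperglycemia paragraph:** make the last step discontinuation of ACTHar gel, with a taper at the Site PI's discretion. Visit 8 already describes one: "Sites will start the ACTHar Gel wean at 40 units and reduce over a 2 week taper period". In Group 2 the Site PI decides whether tacrolimus continues, and the decision is recorded.
- **One added sentence:** patients who stop a study drug attend all remaining scheduled visits (AE/SAE, CMP with eGFR, UP/Cr) through Visit 13 unless they withdraw consent.
- **Visit 8:** word it for all randomized patients still in follow-up at month 12, whether or not they completed 52 weeks of therapy. Visit 13 can stay as it is.

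The cost is a few sentences in an amendment. The visits and their travel are already planned for every patient, though an individual may be asked to travel for up to 21 months after stopping ACTHar gel. Off-drug values will enter the month 12 and month 24 comparisons, which intention to treat already accepts. Some Group 2 patients may be on tacrolimus alone for a time, so the regimen at each visit must be documented.
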